**Analysis will be performed separately for each HCV subtype and treatment duration within each listing**

**Analysis 1:** The following analyses will be performed for subjects who enroll in South Korea:

- A listing of all baseline polymorphisms ( $\geq 2\%$  detection threshold) at signature amino acid positions for each DAA target (NS3 and NS5A) (ITT population).
- The number and percentage of subjects with baseline polymorphisms at detection-thresholds of  $\geq 2\%$  and  $\geq 15\%$  at signature amino acid positions (ITT population). This table includes prevalence of each baseline polymorphism, and a summary of number of subjects with polymorphisms in NS3 only, in NS5A only, any in NS3, any in NS5A, any in NS3 or NS5A, any in NS3 and NS5A.
- Total number and percentage of subjects with baseline polymorphisms *at the key subset of amino acid positions* in NS3 only, in NS5A only, any in NS3, any in NS5A, any in NS3 or NS5A, any in NS3 and NS5A (ITT population) by genotype, subtype, and total.

**Analysis 2:** The impact of baseline polymorphisms on treatment outcome will be assessed for **mITT-GT-VF** population for subjects who enroll in South Korea as follows: for each polymorphism, the SVR12 rate will be calculated for subjects with and without the polymorphism and the 2 rates will be compared using Fisher's exact test. Analysis will be grouped by HCV subtype, treatment duration, and DAA target (NS3 or NS5A). The following will be included in the analyses of impact of baseline polymorphisms on treatment outcome:

- Polymorphisms at signature amino acid positions (vs. no polymorphisms at that position), using detection thresholds of both  $\geq 2\%$  and  $\geq 15\%$ . The analysis will include the number of subjects with polymorphisms in NS3 only, in NS5A only, any in NS3, any in NS5A, any in NS3 or NS5A, any in NS3 + NS5A.

- Each polymorphism at signature amino acid position (vs not that polymorphism) using detection thresholds of  $\geq 2\%$  and  $\geq 15\%$ . The analysis will include the number of subjects with polymorphisms in NS3 only, in NS5A only, any in NS3, any in NS5A, any in NS3 or NS5A, any in NS3 + NS5A.

### **Analysis 3:**

In subjects who enroll in South Korea, the SVR12 rate will be calculated and compared using Fisher's exact test between subjects with or without polymorphisms at 15% detection threshold in NS3 only, in NS5A only, any in NS3, any in NS5A, any in NS3 or NS5A, any in NS3 and NS5A at the *key subset of amino acid positions*. Analysis will be performed by HCV genotype, subtype, and overall on the mITT-GT-VF population.

### **Analysis 4:**

The following analyses will be performed for subjects who enroll in South Korea who do not achieve SVR12 (with separate summaries for subjects in PVF and non-PVF populations) and have post-baseline resistance data available:

- Listings by subject of all *treatment-emergent substitutions* relative to the baseline amino acid sequences will be provided for each DAA target (NS3 and NS5A).
- Listings by subject of all *substitutions at signature amino acid positions* in a post-baseline time point for each DAA target (NS3 and NS5A).

### **Analysis 5: For subjects who enroll in China who experience virologic failure and have sequence data available, the following analyses will be conducted:**

- A listing of all baseline polymorphisms at signature amino acid positions for each DAA target (NS3 and NS5A).
- Listings by subject of all post-baseline substitutions relative to the baseline amino acid sequence will be provided for each DAA target (NS3 and NS5A).
- Listings by subject of all emerged substitutions, by amino acid position and substitution within a DAA target in a post-baseline sample relative to the

baseline amino acid sequence will be provided for each DAA target (NS3 and NS5A).

- Listings by subject of all post-baseline substitutions at signature amino acid positions relative to the appropriate prototypic reference amino acid sequence will be provided for each DAA target (NS3 and NS5A).

If resistance-associated substitutions are not detected in a given target for a subject at the time of failure/discontinuation, then that target may not be sequenced in subsequent samples from that subject.

### **HCV Genotype/Subtype**

Phylogenetic analysis will be conducted on HCV sequence from all available baseline samples from subjects who enroll in South Korea and genotype 1-infected subjects experiencing virologic failure who enroll in China in order to accurately determine subtype.

Subjects' HCV genotype and subtype may be assessed based on the Inno-LiPA 2.0 Assay used by the Central lab (Covance), the HCV genotype determination by Sanger sequencing a region of NS5B by the Central lab (Covance) and/or from phylogenetic analysis of the full length NS3/4A, and/or NS5A sequences performed by AbbVie. If the phylogenetic analysis is available, then it will be used to determine the subject's HCV genotype and subtype. If it is not available, then the Sanger sequencing assay result will be used to determine the subject's HCV genotype and subtype, if available. Finally, if neither the phylogenetic analysis result nor the Sanger sequencing assay results is available, then the Inno-LiPA assay results will be used to categorize the subject. This subtype information will be presented in summaries of efficacy subgroup analyses. The baseline characteristic summary will use the results from the central laboratory (Sanger sequencing or Inno-LiPA 2.0 Assay [if Sanger sequencing not available]).

A summary of HCV subtype as provided by the central laboratory (Sanger sequencing or Inno-LiPA 2.0 Assay [if Sanger sequencing not available]) versus phylogenetic analysis also will be provided.

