#### **5.1.2 Modified Intention-to-Treat (mITT) Populations**

Sensitivity analyses of SVR12 as described in Section 10.5, when applicable, will be performed on the ITT population modified to exclude subjects of multiple genotypes according to the central laboratory or phylogenetic analyses or subjects who received incorrect duration of treatment due to incorrect classification of GT or treatment experience at screening (mITT-GT), and on the mITT-GT population modified to exclude subjects who did not achieve SVR12 for reasons other than virologic failure (i.e., subjects with reasons other than on-treatment HCV virologic failure and relapse) (mITT-GT-VF).

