## 10.5 Sensitivity Analyses for SVR12

Two-sided 95% CIs for the primary endpoint SVR12 rate will be calculated using both the normal approximation to the binomial distribution and the Wilson score method.

Analyses of the primary endpoint will also be performed on the mITT-GT and mITT-GT-VF populations. Both two-sided 95% normal approximation and Wilson score CIs will be provided for each of these sensitivity analyses.

The analyses described above will also be performed for the geographic region of China.

For each sensitivity analysis, a two-sided 95% CI will be produced only if there are at least 10 subjects in the summary.

Listings of subjects excluded from the mITT-GT and mITT-GT-VF populations will be provided, as applicable.

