### **10.6 Efficacy Subgroup Analysis**

Subgroup analyses will be performed for the primary efficacy endpoint of SVR12.

Within each subgroup, the number and percentage of subjects achieving SVR12 will be calculated for the ITT population. The 2-sided 95% Wilson score CI will be produced if there are at least 10 subjects in the subgroup.

The following subgroups will be analyzed:

- HCV genotype (1, 2, 3, 4, 5, or 6) and available subtype (based on the latest determination of genotype from the baseline sample [by the central laboratory or by phylogenetic analysis, with preference given to the phylogenetic analysis results] at the time of the primary SVR12 analysis);

- Prior HCV treatment history (treatment-naïve or treatment-experienced);
- For treatment-experienced subjects, type of prior treatment experience (IFN- or SOF-based);
- For treatment experienced subjects, type of non-response to previous treatment (on-treatment non-responder or breakthrough, post-treatment relapse, or unknown/other);
- Screening HIV co-infection status (HCV mono-infected or HCV/HIV co-infected);
- IL28B genotype (CC or non-CC);
- Sex (male or female);
- Age (< 65 or ≥ 65 years) and (< 75 or ≥ 75 years);
- Geographic region (China or South Korea);
- Type of Asian descent (Chinese or Korean);
- Baseline BMI (< 30 or ≥ 30 kg/m^2);
- Baseline HCV RNA level (< 1,000,000 or ≥ 1,000,000 IU/mL; < 6,000,000 or ≥ 6,000,000 IU/mL; < 10,000,000 or ≥ 10,000,000 IU/mL);
- Baseline HOMA-IR (< 2 or ≥ 2 mU × mmol/L);
- Baseline platelet count (< 100 or ≥ 100 × 10^9/L);
- Baseline albumin (< 35 or ≥ 35 g/L);
- Baseline alpha fetoprotein (< 20 or ≥ 20 ng/mL);
- Baseline Child-Pugh score (5, 6, or > 6);
- Baseline creatinine clearance (< 60, ≥ 60 to < 90, or ≥ 90 mL/min);
- Baseline eGFR by C-MDRD (< 60, ≥ 60 to < 90, or ≥ 90 mL/min/1.73 m^2);
- History of diabetes (yes/no);
- History of bleeding disorders (yes/no);
- History of depression or bipolar disorder (yes/no);
- History of cardiovascular disease (yes/no);
- Baseline metabolic syndrome (yes/no);
- Injection drug use (yes, within last 12 months; yes, more than 12 months ago; or no);

- Baseline stable opiate substitution use (yes/no);
- Baseline hepato-protectant medication use (yes/no);
- Study drug compliance (yes/no);
- Concomitant use of PPIs (yes/no).

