The summaries described above will be performed for the set of all subjects and for the geographic region of China.

A logistic regression model will be used to explore the associations between each of the subgroup variables and SVR12 by fitting a logistic regression model on all subjects in the mITT-GT-VF population. Among all candidate predictors, continuous measurements will be used where possible (e.g., continuous baseline log10 HCV RNA level, continuous age, continuous BMI) in the logistic regression model. A stepwise logistic regression approach will be used to assess the strength of each subgroup variable in predicting SVR12, with a significance level of 0.10 to enter and remain in the model.

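### In China only GT1 virologic failures get baseline phylogenetic genotyping, so membership of mITT-GT, mITT-GT-VF and the genotype subgroups depends on outcome

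*SAP*

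**What the plan says.** SAP Section 10.8 (HCV Genotype/Subtype) runs phylogenetic analysis on available "baseline samples from subjects who enroll in South Korea and genotype 1-infected subjects experiencing virologic failure who enroll in China". It ranks that result first: "If the phylogenetic analysis is available, then it will be used to determine the subject's HCV genotype and subtype". Sanger sequencing comes next and Inno-LiPA last.

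Two rules use the result:

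- **Analysis sets.** Section 5.1.2 forms mITT-GT by modifying the ITT population to "exclude subjects of multiple genotypes according to the central laboratory or phylogenetic analyses or subjects who received incorrect duration of treatment", the second branch applying where genotype or treatment experience was misclassified at screening. mITT-GT-VF is mITT-GT without non-responders whose reason was not virologic failure.
- **Subgroups.** Section 10.6 takes the genotype from the latest determination on the baseline sample, "by the central laboratory or by phylogenetic analysis, with preference given to the phylogenetic analysis results".

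Section 10.5 states: "Analyses of the primary endpoint will also be performed on the mITT-GT and mITT-GT-VF populations". It repeats this for China. Section 10.6 also explores predictors of SVR12 by "fitting a logistic regression model on all subjects in the mITT-GT-VF population".

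Section 10.8 adds baseline sequencing for subjects lost to follow-up before 6 weeks of therapy while not suppressed, which appears to include GT1 subjects from China. These are also SVR12 non-responders. Nothing gives a China responder, or a China subject typed as GT2 to GT6, a baseline phylogenetic test.

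**The concern.** Genotype is a baseline characteristic, so a set or subgroup defined by it should not depend on how the subject responded. In South Korea it does not, because every available baseline sample is sequenced. In China, failure triggers the test.

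Take two treatment-experienced subjects in China, both typed GT1 by the central laboratory, both treated for 12 weeks, and both in truth GT3. The one who fails is sequenced, found to be GT3, judged to have had the wrong duration, and removed from mITT-GT. The one who responds is not sequenced and stays in as a GT1 success.

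The sets affected are mITT-GT, mITT-GT-VF, their China versions, the regression on mITT-GT-VF, and the genotype/subtype subgroups. The China results carry some weight: SAP Section 12.1 says that the regulator requires analyses of the China subset. A sensitivity analysis that this rule can move only in the favourable direction is a weaker check on the ITT result than it appears.

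**Working it through.** **Inputs**

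- SVR12 of 95% among 160, that is 152/160 (SAP Section 4.3).
- China enrolment 60 + 36 + 24 = 120, of whom 60 are GT1 (SAP Section 4.2; the GT1 and GT2 figures are minima).
- 16 weeks for treatment-experienced GT3 only, 12 weeks for all others (SAP Figure 1).
- Prior relapse in GT1 with cirrhosis: 1/98 (Protocol Table 6).
- Assumed: 95% also holds in China (114/120) and in China GT1 (57/60), and the 3 China GT1 non-responders are all virologic failures.
- Assumed: a proportion d of China GT1 failures, 1% to 10%, has a phylogenetic result that triggers exclusion. The documents give no such figure.

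**1. The plan's own figure.** 0.95 ± 1.96 × √(0.95 × 0.05/160) gives 91.6% to 98.4%, as stated.

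**2. What triggers exclusion.** Section 5.1.2 does not name the assay that decides whether the genotype was misclassified. Under the ranking in Section 10.8 it is phylogeny where available.

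| Phylogenetic finding in a China GT1 failure | mITT-GT | Subgroup |
|---|---|---|
| Same genotype and subtype | stays | unchanged |
| Another GT1 subtype | stays | moves |
| GT2, 4, 5, 6, or treatment-naïve GT3 | stays (12 weeks was as assigned) | moves |
| Treatment-experienced GT3 | excluded (duration) | moves |
| More than one genotype | excluded | not stated |

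**3. Effect of each exclusion.** One failure leaves the denominator and the numerator is unchanged.

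- Overall mITT-GT: 152/160 = 95.0%; 152/159 = 95.6%; 152/158 = 96.2%. That is about 0.6 points per failure.
- China mITT-GT: 114/120 = 95.0%; 114/119 = 95.8%; 114/118 = 96.6%. That is about 0.8 points per failure.
- mITT-GT-VF, if 4 of the 8 non-responders are virologic failures (assumed): 152/156 = 97.4% becomes 152/155 = 98.1%. If only 2 are and both are excluded, 152/154 = 98.7% becomes 152/152 = 100%, and the regression has no non-responders left.

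**4. Expected shift.** With phylogeny in failures only, expected overall SVR12 is 152/(160 − 3d). With phylogeny in all 60 China GT1 subjects it would be (152 − 57d)/(160 − 60d), which is 95.00% for every d.

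| d | Failures only | All China GT1 |
|---|---|---|
| 1% | 95.02% | 95.00% |
| 2% | 95.04% | 95.00% |
| 5% | 95.09% | 95.00% |
| 10% | 95.18% | 95.00% |

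**5. Number of failures at risk.** Among 60 China GT1 subjects, 60 × 1/98 = 0.6 failures are expected, with probability 1 − (97/98)^60 = 46% of at least one. At 2% the figures are 1.2 and 70%; at 5% they are 3 and 95%. Step 4 therefore sits at the high end of this range.

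**6. Subgroups.** If one failure is retyped, China GT1 goes from 57/60 = 95.0% to 57/59 = 96.6%. A receiving group of 10 responders (assumed size) goes from 10/10 = 100% to 10/11 = 90.9%.

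**The case against.** The strongest reply is that little depends on this. The primary and secondary analyses use ITT, no hypothesis is tested, and the regression is exploratory. Mixed infections found at screening are already excluded for everyone (Protocol Section 5.2.2, criterion 4). At 0.6 expected failures and d of 1% to 10%, the expected number of exclusions is 0.006 to 0.06. At 0.8 points each, the expected China shift is about 0.005 to 0.05 points. The plan also lists everyone excluded from the mITT sets (Section 10.5) and tabulates central-laboratory against phylogenetic subtype (Section 10.8), so a reader could spot and reverse an exclusion. Finally, Protocol Section 8.1 itself names phylogenetic analyses in defining mITT-GT.

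All of this stands as to size. It does not answer the asymmetry. The listings show a failure that was removed; they cannot show responders who would have been removed if tested. The protocol's definition does not require that phylogeny be run selectively by outcome.

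Two stronger readings are tempting and unsupported. A reader might infer that the genotype-specific rates are all biased upward. They are not: a retyped failure moves, so one group rises and another falls. A reader might also infer that any China GT1 failure can be dropped. The table in step 2 of the working shows that most kinds of retyping leave the subject in mITT-GT.

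**Conclusion.** The point holds in a limited form. In China, phylogenetic genotype is ascertained because of non-response, and it then governs membership of mITT-GT, mITT-GT-VF and the genotype/subtype subgroups. For the two mITT sets, including their China versions and the regression, the effect is zero or upward. It is about 0.6 points overall or 0.8 points in China for each failure excluded from mITT-GT, and about 0.02 to 0.18 points overall in expectation. That expectation rests on an assumed discordance of 1% to 10% and an assumed 3 China GT1 failures; at the earlier relapse rate of 1/98 it would be smaller. Subgroup membership depends on outcome too, with no single direction. The primary ITT SVR12 estimate and its interval do not change. The reason to act is the one-sided rule applied to very few failures, not a large average bias.

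**What to change.** For subjects enrolled in China, base the genotype part of the mITT-GT exclusions and the genotype/subtype subgroups on the central-laboratory result (Sanger, otherwise Inno-LiPA). Apply the phylogenetic override only in South Korea, where all available baseline samples are sequenced whatever the outcome. Leave the exclusion for misclassified treatment experience as it is. Show the China phylogenetic results only in the planned central-laboratory versus phylogeny summary and in listings. Sections 5.1.2, 10.6 and 10.8 need matching wording, and the departure from Protocol Section 8.1 needs an entry in SAP Section 12.1.

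The same edit should reconcile the full-length sequences that Section 10.8 describes for phylogeny with the partial regions it specifies for China (NS3 1–181, NS5A 1–215).

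The cost is SAP text only. The central-laboratory genotype already exists for every subject and already serves the baseline summary described in Section 10.8. The downsides are small: less precise subtyping of the few China failures in the subgroup tables, and a genotype basis that differs by country. Sequencing every China baseline sample would also remove the asymmetry, but it means additional laboratory work.

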### **HIV Drug-Resistance Analyses**

If any subject on stable HIV-1 ART develops a confirmed, quantifiable plasma HIV-1 RNA level (HIV-1 RNA  $\geq$  200 copies/mL at one assessment and  $\geq$  500 copies/mL on repeat testing) after starting the study, the HIV-1 protease, reverse transcriptase and/or integrase sequences, as applicable, will be analyzed by Monogram Biosciences using the GenoSure® Prime drug resistance assays for subjects from South Korea. The number of subjects who demonstrate HIV genotypic resistance and the genotypic resistant mutations detected in the samples obtained from these subjects will be tabulated and summarized in the final CSR, as applicable. Resistance will be defined as described by the IAS-USA Panel.

#### **10.9 Patient Reported Outcomes**

The following instruments will be used to collect patient reported outcomes (PROs): EuroQol-5 Dimensions-3 Level (EQ-5D-3L) and Fatigue Severity Scale (FSS).

Subject's responses to the EQ-5D-3L will be combined into a unique health state using a 5-digit code with 1 digit from each of the 5 dimensions. The EQ-5D-3L states will be converted into a single preference-weighted health utility index score by applying weights. The VAS score will be analyzed separately. For EQ-5D-3L index and VAS scores, no imputation will be performed for missing items.

The FSS measures the impact of fatigue over the past week on specific types of functioning. The survey consists of 9 questions using a 7-point Likert scale. A total score is calculated as the average of the individual item responses (adding up all the answers and dividing by nine). Higher FSS scores indicate a higher degree of impact of fatigue. Imputation will be applied to the total score as described in Section 6.3.

Summary statistics (n and mean) at each visit and for change from baseline (n, mean, SD, minimum and maximum) to each visit will be provided for EQ-5D-3L health index score and VAS score and for the FSS total score.

The number and percentage of subjects who have ever experienced an increase from baseline in the FSS total score of greater than or equal to 0.7 through each applicable timepoint will also be calculated, along with two-sided 95% CIs based on the normal approximation to the binomial distribution.

If a subject starts another treatment for HCV, then all PRO values for this subject measured on or after the start date of the new HCV treatment will be excluded from analyses.

The ITT population will be used to perform the analyses described above for the set of all subjects and for the geographic region of China.

## **11.0 Safety Analysis**

### **11.1 General Considerations**

Safety data will be summarized using the safety population. Safety data will be summarized for the set of all subjects and for the geographic region of China.

### **11.2 Analysis of Adverse Events**

Adverse events (AEs) will be coded using the MedDRA coding dictionary. The actual version of the MedDRA coding dictionary will be noted in the CSR.

HIV-1-infected subjects participating in clinical trials may develop infections typically associated with AIDS. A list of these known AIDS-associated opportunistic infections (OIs) is contained in Appendix D of the study protocol. AEs that are identified by the investigators as AIDS-associated OIs will not be included in any analyses of AEs, but will be summarized separately for the HCV/HIV co-infected subjects.

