6.1.1.2 Serious Adverse Events

If an AE meets any of the following criteria, it is to be reported to AbbVie as a serious adverse event (SAE) within 24 hours of the site being made aware of the SAE.

Death of Subject	An event that results in the death of a subject.
Life-Threatening	An event that, in the opinion of the investigator, would have resulted in immediate fatality if medical intervention had not been taken. This does not include an event that would have been fatal if it had occurred in a more severe form.
Hospitalization or Prolongation of Hospitalization	An event that results in an admission to the hospital for any length of time or prolongs the subject's hospital stay. This does not include an emergency room visit or admission to an outpatient facility.
Congenital Anomaly	An anomaly detected at or after birth, or any anomaly that results in fetal loss.
Persistent or Significant Disability/Incapacity	An event that results in a condition that substantially interferes with the activities of daily living of a study subject. Disability is not intended to include experiences of relatively minor medical significance such as headache, nausea, vomiting, diarrhea, influenza, and accidental trauma (e.g., sprained ankle).

Important Medical Event Requiring Medical or Surgical Intervention to Prevent Serious Outcome

An important medical event that may not be immediately life-threatening or result in death or hospitalization, but based on medical judgment may jeopardize the subject and may require medical or surgical intervention to prevent any of the outcomes listed above (i.e., death of subject, life-threatening, hospitalization, prolongation of hospitalization, congenital anomaly, or persistent or significant disability/incapacity). Additionally, any elective or spontaneous abortion or stillbirth is considered an important medical event. Examples of such events include allergic bronchospasm requiring intensive treatment in an emergency room or at home, blood dyscrasias or convulsions that do not result in inpatient hospitalization, or the development of drug dependency or drug abuse.

For SAEs with the outcome of death, the date and cause of death will be recorded on the appropriate case report form.

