6.1.4 Adverse Event Collection Period

All SAEs as well as protocol-related nonserious AEs (e.g., infection at liver biopsy site) will be collected from the time the subject signed the study-specific informed consent until study drug administration. From the time of study drug administration until 30 days following discontinuation of study treatment has elapsed, all AEs will be collected, whether solicited or spontaneously reported by the subject. After 30 days following completion of study treatment and throughout the Post-Treatment Period, all spontaneously reported SAEs will be collected (nonserious AEs will not be collected).

Adverse event information will be collected as shown in [Figure 3](#).

Figure 3. Adverse Event Collection

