6.1.5 Adverse Event Reporting

In the event of a SAE, whether associated with study drug or not, the Investigator will notify Clinical Pharmacovigilance within 24 hours of the site being made aware of the SAE by entering the SAE data into the electronic data capture (EDC) system. SAEs that occur prior to the site having access to the RAVE[®] system, or if RAVE is not operable, should be documented on the SAE Non-CRF forms and emailed (preferred route) or faxed to Clinical Pharmacovigilance within 24 hours of the site being made aware of the SAE.

Email:
FAX to

For safety concerns, contact the Antiviral Safety Team at:

Antiviral Safety Team

[name]
[name]

Office:
Fax:
Email:

For any subject safety concerns, please contact the physician listed below:

Primary Therapeutic Area Medical Director:

In emergency situations involving study subjects when the primary TA MD is not available by phone, please contact the 24-hour AbbVie Medical Escalation Hotline where your call will be re-directed to a designated backup AbbVie TA MD:

Phone:

AbbVie will be responsible for Suspected Unexpected Serious Adverse Reactions (SUSAR) reporting for the Investigational Medicinal Product (IMP) in accordance with Directive 2001/20/EC. The reference document used for SUSAR reporting in the EU countries will be the most current version of the Investigator's Brochure.

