6.1.8 Collection of Data Regarding Known AIDS-Associated Opportunistic Infections

HIV-1 infected subjects participating in clinical trials may develop infections typically associated with AIDS. These known AIDS-associated opportunistic infections (OI) are listed in [Appendix D](#).³⁸ The events listed in [Appendix D](#) will be summarized as HIV related events, not as AEs. These OIs will be collected from the time of study drug administration until 30 days following discontinuation of study drug.

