### **AIDS-Associated Opportunistic Infections**

The number and percentage of subjects experiencing treatment-emergent AIDS-associated OIs will be tabulated according to SOC and preferred term for the HCV/HIV co-infected subjects (determined at Screening). Subjects reporting more than one AIDS-associated OI for a given preferred term will be counted only once for that term. Subjects reporting more than one AIDS-associated OI within a SOC will be counted only once for that SOC. Subjects reporting more than one AIDS-associated OI will be counted only once in the overall total.

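### Serious, Grade 3+, drug-stopping or fatal AIDS-associated opportunistic infections are left out of the matching adverse event rows, and the separate infection table does not carry that information

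*SAP*

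**What the plan says.** SAP 11.2 sets the rule for the whole AE section: "AEs that are identified by the investigators as AIDS-associated OIs will not be included in any analyses of AEs". The sentence goes on: "but will be summarized separately for the HCV/HIV co-infected subjects". Protocol 6.1.8 agrees. The events in Appendix D "will be summarized as HIV related events, not as AEs", and "These OIs will be collected from the time of study drug administration until 30 days following discontinuation of study drug".

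The replacement output is described in SAP 11.2.2, under AIDS-Associated Opportunistic Infections: "The number and percentage of subjects experiencing treatment-emergent AIDS-associated OIs will be tabulated according to SOC and preferred term", for the co-infected subjects. SAP 11.2.3 adds a listing of treatment-emergent OIs.

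The AE overview in SAP 11.2.2 has rows for serious events, Grade 3 or higher events, events leading to discontinuation, to interruption and to death, and a separate row for deaths. It is produced for all subjects, for China, and for the co-infected subjects within each.

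On collection, Protocol 6.1.4 says: "After 30 days following completion of study treatment and throughout the Post-Treatment Period, all spontaneously reported SAEs will be collected". Protocol 6.1.5 says: "In the event of a SAE, whether associated with study drug or not, the Investigator will notify Clinical Pharmacovigilance within 24 hours". Neither section mentions OIs.

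The trial plans at most 16 co-infected subjects out of about 160 (Protocol 5.1, SAP 4.2). SAP 12.1 anticipates fewer co-infected subjects than the protocol expected, without giving a figure.

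**The concern.** Keeping HIV-related infections out of routine AE tables is a reasonable convention when the aim is to separate background HIV morbidity from possible drug effects. The difficulty is that this exclusion reaches the rows that describe serious harm. Safety is a primary objective (Protocol 4.1, SAP 4.1). A reader of the co-infected overview will take its serious-event row as the count of serious events in that group. If a co-infected subject is hospitalised with an OI, that row does not include the event, and nothing specified for the OI table tells the reader that it was serious.

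**Working it through.** The plan states no figure for this point, so there is none to reproduce. The check has three parts.

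**1. Follow one case through the outputs.** Take a co-infected subject with a treatment-emergent OI that is serious, Grade 4, leads to discontinuation and is fatal.

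| Output | SAP section | Does the case count? |
|---|---|---|
| Overview rows: any, serious, Grade 3+, leading to discontinuation, leading to death | 11.2.2 | No |
| Tables by organ class and preferred term, and by preferred term | 11.2.2 | No |
| AE table by ART regimen | 11.2.2 | No |
| OI table | 11.2.2 | Yes, but without seriousness, grade, relationship or outcome |
| OI listing | 11.2.3 | Yes; columns not specified |
| All-SAE listing | 11.2.3 | Unclear: depends on whether a listing is an analysis of AEs |
| Deaths row | 11.2.2 | Yes, without the cause |
| Discontinuation by reason | 8.1 | Yes, without naming the OI |

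An OI that leads only to interruption is likewise missing from the interruption row. It would be counted among interruptions in SAP 8.1.

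**2. Size.** The SAP gives counts and percentages for AEs. The intervals below are added for scale, using the Wilson score method with z = 1.96:

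centre = (x + z²/2)/(n + z²); half-width = z·√[p(1−p)/n + z²/(4n²)] / (1 + z²/n)

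- Planned rule, one serious OI among 16: 0/16 = 0%. The upper limit is 3.84/(16 + 3.84) = 19.4%.
- Same event counted: 1/16 = 6.3%. Centre (1 + 1.92)/19.84 = 14.7%, half-width 13.6%, so 1.1% to 28.3%.
- In all 160 subjects, with no other event: 0/160 (0 to 2.3%) against 1/160 = 0.6% (0.1 to 3.5%).

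The documents give no OI incidence. **Assumption:** a per-subject risk r of any OI over the reporting window, from 0.5% to 5%. The chance of at least one OI is 1 − (1 − r)ⁿ.

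| r | n = 16 | n = 8 |
|---|---|---|
| 0.5% | 7.7% | 3.9% |
| 1% | 14.9% | 7.7% |
| 2% | 27.6% | 14.9% |
| 5% | 56.0% | 33.7% |

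Serious OIs are a subset, so the chance that this rule changes a serious-event row is lower than these figures.

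**3. Collection period.** Protocol 6.1.8 stops OI collection 30 days after study drug. Protocol 6.1.4 continues SAE collection through the 24-week (168-day) Post-Treatment Period. The two sections differ over 168 − 30 = 138 days, or 138/168 = 82% of follow-up. SAP 11.2.1 also ends the treatment-emergent window at 30 days, so this difference does not affect the treatment-emergent tables. It bears on the listing of all serious AEs through the end of the study.

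**The case against.** The strongest answer is that the protocol and SAP agree on a prespecified convention and that the event stays visible. With no more than 16 co-infected subjects, a single OI would stand out in its own table and listing. A death would be in the Deaths row, a discontinuation in the disposition summary, and loss of HIV control in the SAP 11.6 analysis and listing. Eligibility also limits the risk: Protocol 5.2.1 sets CD4+ thresholds and, for those on ART, HIV-1 RNA below LLOQ, while 5.2.2 excludes recent AIDS-defining events and recent OI treatment or prophylaxis. SAP 11.2.3 specifies columns for none of its AE listings, so it cannot be said that the OI listing will lack grade or outcome.

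All of this stands, and it limits the consequence. It does not correct the serious-event rows, and it does not add seriousness or outcome to the OI table.

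A reader might also infer more than the documents support:

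- *That the 30-day limit removes OIs from the AE tables.* It does not, because those tables use the same limit.
- *That a serious OI is neither an SAE nor collected after day 30.* The wording in Protocol 6.1.8 about AEs governs how OIs are summarised. The AE definition in 6.1.1.1 is broad enough to include them, SAP 11.2 itself calls them AEs, and 6.1.4 and 6.1.5 make no exception. What remains is an unreconciled difference between 6.1.8 and 6.1.4.
- *That the SAE total would be understated by a sizeable fraction, scaled from the 4/274 in Protocol 3.0.* That rate comes from Phase 2 Part 1 arms at mixed doses, some with ribavirin; Protocol 3.0 reports the safety data in cirrhosis separately, from Part 2. It is not an expected rate for this all-cirrhotic trial.

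**Conclusion.** The point holds as a reporting defect of limited size. By the letter of SAP 11.2, a treatment-emergent OI that is serious, Grade 3 or higher, drug-stopping, drug-interrupting or fatal is absent from the AE rows and tables meant to show such events. One serious case in the maximum co-infected group would read 0/16 rather than 1/16 (6.3%). With fewer co-infected subjects, each event is a larger share.

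This rests on SAP 11.2 being applied literally and on at least one qualifying OI occurring, for which the documents give no probability. The efficacy results are unaffected. The documents do not show that such events would go uncollected, unexpedited or wholly unreported. Separately, Protocol 6.1.8 and 6.1.4 give different collection periods for a serious OI starting after day 30 and should be reconciled.

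**What to change.** - **SAP 11.2 and 11.2.2:** keep the separate OI table. Add that OIs which are serious, Grade 3 or higher, fatal, or lead to discontinuation or interruption are also counted in the corresponding AE overview rows and tables, flagged and footnoted as OIs.
- **SAP 11.2.3:** apply the same rule to the matching listings, which settles whether the exclusion covers listings. Specify seriousness, grade, relationship and outcome as columns of the OI listing.
- **Protocol 6.1.8 and 6.1.4:** add a cross-reference stating which collection period applies to a serious OI starting more than 30 days after the last dose.

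The cost is SAP wording, a flag in existing programs, a footnote and one reconciling sentence in the protocol. The drawback is that SAE and Grade 3+ counts may be slightly higher and will include HIV-related events. The flag lets a reader set those aside.
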